6.4.1.3. Very Low Disease Activity (VLDA)

VLDA is defined based on the same 7 criteria as in MDA. A subject will be classified as having achieved VLDA when all 7 out of 7 of the criteria are met. In the case that some of the VLDA components are missing, the VLDA assessment will be based on the nonmissing components. If nonmissing components are not sufficient to determine the VLDA response, then the VLDA response will be considered as missing.

6.4.1.4. Disease Activity Index for Psoriatic Arthritis (DAPSA), DAPSA LDA, DAPSA remission and Time to Achieve DAPSA LDA

$DAPSA = TJC68 + SJC66 + PGADA (0 - 100 \text{ VAS})/10 + PGAPI (0 - 100 \text{ VAS})/10 + CRP$ (mg/dL).

where

PGADA = Patient's Global Assessment of Disease Activity (0 – 100 VAS);

PGAPI = Patient's Global Assessment of PsA Pain Intensity (0 – 100 VAS);

CRP is in unit of mg/dL.

If any of the components is missing, then DAPSA remains missing.

The derived DAPSA binary parameters include:

- DAPSA remission: $DAPSA \leq 4$,
- DAPSA LDA: $DAPSA \leq 14$.

The time to achieve DAPSA LDA is defined as:

Date of first (DAPSA \leq 14) – First dose date of any study drug + 1

For each subject included in the analysis, all available measurement for DAPSA will be considered for the time to achieve DAPSA LDA based on the treatment policy estimand.

The time to achieve DAPSA LDA can be derived for the subject in each treatment group based on the data during Main study phase. If the DAPSA LDA is not achieved during Main study phase, the time to achieve DAPSA LDA will be censored at the last nonmissing DAPSA assessment date during Main study phase. If the component scores of DAPSA are at different dates for a visit, the latest date will be used for the derivation of time to achieve DAPSA LDA.

6.4.1.5. Physician's Global Assessment of Psoriasis (PhGAP)

The physician will give a score on the subject's psoriasis disease activity, according to the following grades:

- Induration (I) (0 – 5 scale, averaged over all lesions),
- Erythema (E) (0 – 5 scale, averaged over all lesions),
- Scaling (S) (0 – 5 scale, averaged over all lesions).

The sum of the 3 grades will be divided by 3, i.e., $= (I + E + S)/3$, and rounded to the nearest integer (i.e., 0, 1, 2, 3, 4, 5) to obtain the total average score. Physician's Static Global Assessment (0 – 5 scale) will be based on the total average score: 0 = cleared; 1 = minimal; 2 = mild; 3 = moderate; 4 = marked; and 5 = severe.

If any of the grades above is missing, then the score remains missing.

Physician's Static Global Assessment (0-5 scale) will be the endpoint for analysis, which will be considered as continuous endpoint. The summaries and analyses will be conducted on the FAS subjects with psoriasis covering at least 3% of the BSA at Baseline.

6.4.1.6. Modified Nail Psoriasis Area and Severity Index (mNAPSI)

mNAPSI is used to assess each nail abnormality for each of subject's nail. Three features or groups of features (pitting, onycholysis together with oil-drop dyschromia, and crumbling) of each fingernail will be graded on a scale from 0 to 3. Four features (leukonychia, splinter hemorrhages, hyperkeratosis, and red spots in the lunula) will be graded as either present (1) or absent (0) for each fingernail. Each finger will have a score between 0 and 13. The total mNAPSI score is the sum of all abnormalities individual score across all fingers, and the total mNAPSI score ranges from 0 to 130.

In case of one or more missing digits, the available digits will be used to calculate mNAPSI.

The summaries and analyses of nail psoriasis will be conducted on the FAS subjects who had psoriatic nail involvement at Baseline.

6.4.1.7. 12-item Psoriatic Arthritis Impact of Disease (PsAID-12)

The PsAID is calculated based on 12 numerical rating scales (NRS) questions. Each NRS is assessed as number between 0 and 10.

PsAID final value

$$\begin{aligned} &= (\text{PsAID1 (pain) NRS} \times 3) + (\text{PsAID2 (fatigue) NRS} \times 2) + \\ &(\text{PsAID3 (skin) NRS} \times 2) + (\text{PsAID4 (work and / or leisure activities) NRS} \\ &\times 2) + (\text{PsAID5 (function) NRS} \times 2) + (\text{PsAID6 (discomfort) NRS} \times 2) + (\\ &\text{PsAID7 (sleep) NRS} \times 2) + (\text{PsAID8 (coping) NRS} \times 1) + (\text{PsAID9 (anxiety)} \\ &\text{NRS} \times 1) + (\text{PsAID10 (embarrassment) NRS} \times 1) + (\text{PsAID11 (social life)} \\ &\text{NRS} \times 1) + (\text{PsAID12 (depression) NRS} \times 1) \end{aligned}$$

The total is divided by 20. Thus the range of the final PsAID value is 0-10 where higher figures indicate worse status.

If one of the 12 NRS values composing the PsAID is missing, the imputation is as follows: calculate the mean value of the 11 other (nonmissing) NRS (range, 0 – 10), impute this value for the missing NRS. Then, calculate the PsAID as explained above. If 2 or more of the NRS are missing, the PSAID is considered missing value (no imputation).

6.4.1.8. ACR70

ACR70 is similarly defined as ACR20 (see Section 6.2.1), except that the improvement threshold from Baseline is 70%.

6.4.1.9. Disease Activity Score for 28 joint count using C-reactive protein (DAS28 (CRP)), DAS28 (CRP) LDA, DAS28 (CRP) remission and Time to Achieve DAS28(CRP) LDA

The DAS28(CRP) score is calculated as follows:

$$\text{DAS28(CRP)} = 0.56\sqrt{\text{TJC28}} + 0.28\sqrt{\text{SJC28}} + 0.36\ln(\text{CRP} + 1) + 0.014 \times \text{PGADA} + 0.96,$$

where

$\ln(\text{CRP} + 1)$ is the natural logarithm of (CRP value [mg/L] + 1);

PGADA is on 0 – 100 scale.

Higher DAS28 (CRP) value indicates more severe disease activity.

If any of the components is missing, the DAS28(CRP) will be set as missing.

The derived DAS28(CRP) binary parameters include:

- DAS28(CRP) remission: $\text{DAS28(CRP)} < 2.6$,
- DAS28(CRP) LDA: $\text{DAS28(CRP)} \leq 3.2$.

The time to achieve DAS28(CRP) LDA is defined as:

Date of first $[\text{DAS28(CRP)} \leq 3.2]$ – First dose date of any study drug + 1

For each subject included in the analysis, all available measurement for DAS28(CRP) will be considered for the time to achieve DAS28(CRP) LDA based on the treatment policy estimand.

The time to achieve DAS28(CRP) LDA can be derived for the subject in each treatment group based the data during Main study phase. If the DAS28(CRP) LDA is not achieved during Main study phase, the time to achieve DAS28(CRP) LDA will be censored at the last nonmissing DAS28(CRP) assessment date during Main study phase. If the component scores of DAS28(CRP) are at different dates for a visit, the latest date will be used for the derivation of time to achieve DAS28(CRP) LDA.

6.4.1.10. Psoriatic Arthritis Response Criteria (PsARC) response

PsARC responder is defined as having an improvement in at least 2 of the 4 factors (with at least one factor being a joint count) and no worsening in the remaining factors:

- TJC68 (improvement defined as a decrease from baseline of at least 30%),
- SJC66 (improvement defined as a decrease from baseline of at least 30%),
- PGADA (0 – 100 VAS, improvement defined as a decrease from baseline of at least 20),
- PhGADA (0 – 100 VAS, improvement defined as a decrease from baseline of at least 20).

In the case that some of the PsARC components are missing, the PsARC assessment will be based on the nonmissing components. If nonmissing components are not sufficient to determine the PsARC response, then the PsARC response will be considered as missing.

6.4.1.11. PASI50, PASI90, PASI100

PASI50, PASI90 and PASI100 response are defined similarly as PASI75, except that the improvement threshold from baseline are 50%, 90% and 100% in PASI score, respectively.

6.4.1.12. Spondyloarthritis Research Consortium of Canada (SPARCC) Enthesitis Index

The enthesitis examination is based on the 16 anatomical sites: the medial epicondyle (left and right), the lateral epicondyle (left and right), the supraspinatus insertion (left and right), the bilateral greater trochanter (left and right), the quadriceps tendon insertion into superior border of patella (left and right), the patellar ligament insertion into inferior pole of patella or tibial tuberosity (left and right), the achilles tendon insertion (left and right), and the plantar fascia insertion (left and right). Enthesitis at each site was scored on a dichotomous basis: 0 means Enthesitis Absent and 1 means Enthesitis Present.

SPARCC Enthesitis Index is derived as the sum of the enthesitis score over the 16 sites mentioned above.

If there are missing items, then available data are used to derive SPARCC Enthesitis Index.

The summaries and analyses of SPARCC Enthesitis Index will be conducted on the FAS subjects with enthesitis at Baseline.

6.4.2. Analysis Methods for Other Secondary Endpoints

The FAS will be used for all summaries and analyses of other secondary efficacy endpoints.

For the binary endpoints of the ACR20 response, the ACR50 response, the PASI75 response in subjects with psoriasis covering $\geq 3\%$ of the BSA at Baseline and the MDA response, for subjects with observed outcome, the similar analysis as the key secondary endpoint analyses described in Section 6.3.2 will be applied. The proportions of subjects achieving above endpoints (observed case) will be plotted over time during Main study by treatment and by visit.

For all the other binary endpoints, only above mentioned observed response rate, 2-sided 95% CI and non-stratified response rate difference along with its 95% CI will be provided by visit.

For all the continuous endpoints, absolute value and change from Baseline will be summarized using descriptive statistics (sample size, mean, SD, median, Q1, Q3, minimum, and maximum) by treatment and by visit.

For the continuous endpoints of the change from baseline in HAQ-DI, the change from Baseline in SF-36v2 PCS, the change from Baseline in LEI for subjects with enthesitis at Baseline, the change from Baseline in FACIT-Fatigue and the change from Baseline in LDI for subjects with dactylitis at Baseline, plots of mean \pm SD for change from baseline by visit will be presented.

For time to event analyses, Kaplan-Meier plot of each treatment group during Main study will be provided. Number of subjects having events and censored, KM estimates of median (95% CI), Q1, Q3, minimum and maximum of the time to events will be summarized by treatment group.

The by-subject listing of each endpoint and corresponding components, if available, including data during the Main Study and LTE phases will be provided.

6.5. Changes From Protocol-Specified Efficacy Analyses

Due to study termination and insufficient number of subjects enrolled, graphical approach of multiple test procedures will not be implemented, and only the nominal p values will be presented.

Due to small number of subjects available, for key secondary binary endpoints, logistic regression analyses may not be applicable. In such cases, no p-value will be provided. For key secondary continuous endpoints, MMRM analyses may not be applicable. In such cases, only descriptive summary statistics will be provided.

No sensitivity analyses will be performed.

7. SAFETY ANALYSES

7.1. Adverse Events and Deaths

7.1.1. Adverse Event Dictionary

Clinical and laboratory adverse events (AEs) will be coded using the current version of MedDRA. System organ class (SOC), high-level group term (HLGT), high-level term (HLT), preferred term (PT), and lower-level term (LLT) will be provided in the AE dataset.

7.1.2. Adverse Event Severity

Adverse events are graded by the investigator as Grade 1, 2, 3, 4, or 5 according to toxicity criteria specified in the protocol. The severity grade of events for which the investigator did not record severity will be categorized as “missing” for tabular summaries and data listings. The missing category will be listed last in summary presentation.

7.1.3. Relationship of Adverse Events to Study Drug

Related AEs are those for which the investigator selected “Related” on the AE CRF to the question of “Related to Study Treatment.” Relatedness will always default to the investigator’s choice, not that of the medical monitor. Events for which the investigator did not record relationship to study drug will be considered related to study drug for summary purposes. However, by-subject data listings will show the relationship as missing.

7.1.4. Serious Adverse Events

Serious adverse events (SAEs) will be identified and captured as SAEs if the AEs met the definitions of SAEs that were specified in the study protocol. SAEs captured and stored in the clinical database will be reconciled with the SAE captured in Gilead safety database before data finalization.

7.1.5. Treatment-Emergent Adverse Events

7.1.5.1. Definition of Treatment-Emergent Adverse Events

Treatment-emergent adverse events (TEAEs) are defined as one or both of the following:

- Any AEs with an onset date on or after the study drug start date and no later than 30 days after permanent discontinuation of study drug
- Any AEs leading to premature discontinuation of study drug.

For subjects who entered LTE, TEAEs with an onset date prior to first dose date of any study drug for LTE will be allocated to the Main Study phase. TEAEs with an onset date on or after the first dose date of any study drug for LTE will be allocated to the LTE phase.

7.1.5.2. Incomplete Dates

If the onset date of the AE is incomplete and the AE stop date is not prior to the first dosing date of study drug, then the month and year (or year alone if month is not recorded) of onset determine whether an AE is treatment emergent. The event is considered treatment emergent if both of the following 2 criteria are met:

- The AE onset is the same as or after the month and year (or year) of the first dosing date of study drug, and
- The AE onset date is the same as or before the month and year (or year) of the date corresponding to 30 days after the date of the last dose of study drug

An AE with completely missing onset and stop dates, or with the onset date missing and a stop date later than the first dosing date of study drug, will be considered to be treatment emergent. In addition, an AE with the onset date missing and incomplete stop date with the same or later month and year (or year alone if month is not recorded) as the first dosing date of study drug will be considered treatment emergent.

For subjects who entered LTE, an AE with incomplete onset date that is prior to the month and year (or year) of the first dose date of any study drug for LTE will be allocated to the Main Study phase. An AE with incomplete onset date that is after the month and year (or year) of the first dose date of any study drug for LTE will be allocated to the LTE phase.

In addition, an AE with completely missing onset date or incomplete onset date that is same as the month and year (or year) of the first dose date of any study drug for LTE, and stop date that is prior to the date (or month and year if day is not recorded; or year alone if month is not recorded) of the first dose date of any study drug for LTE, will be allocated to the Main Study phase. An AE with completely missing onset date or incomplete onset date that is same as the month and year (or year) of the first dose date of any study drug for LTE, and stop date that is missing, or the same as, or after the date (or month and year if day is not recorded; or year alone if month is not recorded) of the first dose of any study drug for LTE will be allocated to the LTE phase.

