1.3. Sample Size and Power

Sample size is determined based on the non-inferiority test of each filgotinib group compared to the adalimumab group on the ACR20 response rate at Week 12. When assuming the ACR20 response rate being 52% and 60% for the adalimumab and each filgotinib group, and 38.6% for the placebo group, 244 subjects in each filgotinib group and placebo group, and 122 subjects in the adalimumab group are required to obtain 90% power at a two-sided 0.025 significance level to demonstrate that filgotinib group preserves more than 50% of the effect of adalimumab with respect to the ACR20 response rate at Week 12.

A sample size of 244 subjects in each filgotinib group and the placebo group will provide over 95% power to detect a difference in ACR20 response rate of 21.4% at Week 12 (38.6% and 60% for the placebo group and each filgotinib group, respectively) using a two-sided 0.025 significance level superiority test.

In summary, the total sample size will be approximately 854 subjects per original planning.

The study was terminated per Sponsor’s decision after 67 subjects had been enrolled. At study termination, 13 out of 67 subjects continued on to the LTE, and 7 of those 13 subjects were terminated immediately after entering LTE phase. All the other subjects were prematurely discontinued from or completed the Main Study visits.

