3. GENERAL CONSIDERATIONS FOR DATA ANALYSES

Analysis results will be presented using descriptive statistics. For categorical variables, the number and percentage of subjects in each category will be presented; for continuous variables, the number of subjects (n), mean, standard deviation (SD) or standard error (SE), median, first quartile (Q1), third quartile (Q3), minimum, and maximum will be presented.

By-subject listings will be presented for all subjects in the All Randomized Analysis Set and sorted by subject identification (ID) number, visit date, and time (if applicable). Data collected on log forms, such as AEs, will be presented in chronological order within the subject. The treatment group to which subjects were randomized will be used in the listings. Age, sex at birth, race, and ethnicity will be included in the listings, as space permits.

Given the small number of subjects who entered LTE phase, for all the efficacy and safety analyses, unless specified otherwise, all the analyses and summary tables will be generated based on the data during Main Study phase (for subjects enrolled under Protocol Amendment (PA) 1 who stayed in Main Study beyond Week 16 visit, only the data up to Week 16 visit will be included). All the data will be presented in the listing.

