7.1.6.1. Summaries of AE Incidence

The number and percentage of subjects who experienced at least 1 TEAE will be provided and summarized by SOC, HLT, PT, and treatment group. For other AEs described below, summaries will be provided by SOC, PT, and the treatment group:

- TEAE (by maximum severity)
- TEAEs with Grade 3 or higher (by maximum severity)

- TE treatment-related AEs (by maximum severity)
- TE treatment-related AEs with Grade 3 or higher (by maximum severity)
- TE SAEs
- TE treatment-related SAEs
- TEAEs leading to premature discontinuation of any study drug
- TEAEs leading to premature discontinuation of study
- TE AEs leading to death (i.e., outcome of death)
- TEAEs leading to temporary interruption of any study drug

A brief, high-level summary of the number and percentage of subjects who experienced at least 1 TEAE in the categories described above will be provided by treatment group. All deaths observed in the Main Study will also be included in this summary.

Multiple events will be counted only once per subject in each summary. Adverse events will be summarized and listed first in alphabetic order of SOC (and HLT within each SOC if applicable), and then by PT in descending order of total frequency within each SOC. For summaries by severity grade, the most severe grade will be used for those AEs that occurred more than once in an individual subject during the study.

In addition to the above summary tables, all TEAEs will be summarized by PT only, in descending order of total frequency.

In addition, data listings will be provided for the following:

- All AEs, indicating whether the event is treatment emergent
- All SAEs
- All Deaths
- All SAEs leading to death (i.e., outcome of death)
- All AEs with severity of Grade 3 or higher
- All AEs leading to premature discontinuation of any study drug
- All AEs leading to premature discontinuation of study
- All AEs leading to temporary interruption of any study drug

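### For LTE entrants, a treatment-emergent AE whose phase cannot be determined is assigned to the LTE and so is counted in no AE summary table

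*SAP*

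**What the plan says.** SAP 7.1.5.2 makes two separate decisions about an AE with an incomplete date.

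- **Treatment emergence.** Doubt is resolved towards counting. "An AE with completely missing onset and stop dates, or with the onset date missing and a stop date later than the first dosing date" is treatment-emergent. So is an AE whose partial onset fits the months (or years) from first dose to 30 days after last dose.
- **Phase, for LTE entrants.** "an AE with incomplete onset date that is prior to the month and year (or year) of the first dose date of any study drug" in the LTE goes to the Main Study; a partial onset after that month and year (or year) goes to the LTE. For the remaining group, "completely missing onset date or incomplete onset date that is same as the month and year (or year) of the first dose date", the stop date decides. If it is earlier than the first LTE dose, the AE goes to the Main Study. The condition "and stop date that is missing, or the same as, or after the date" of that dose sends it to the LTE.

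SAP 3 says that, unless specified otherwise, "all the analyses and summary tables will be generated based on the data during Main Study phase", and adds: "All the data will be presented in the listing". SAP 7.1.6 and 7.1.7 specify no AE table for the LTE. SAP 7.1.6.1 does call for a listing of "All AEs, indicating whether the event is treatment emergent". SAP 1.3 reports that "13 out of 67 subjects continued on to the LTE", and that 7 of those 13 were stopped as soon as they entered it.

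**The concern.** Assigning a doubtful event to the later phase does no harm when both phases are tabulated, because the event is counted in one table or the other. After early termination only the Main Study is tabulated. An event with an indeterminate phase that falls to the LTE is therefore declared treatment-emergent and then counted nowhere.

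This differs from the deliberate decision to leave LTE events to the listings. An event known to have started in the LTE is meant to be outside the tables. The events at issue may have started on randomised treatment, and the documents give no reason for resolving that doubt towards the phase without tables. What is at stake is the completeness of the Main Study tables of TEAEs, serious AEs, AEs of special interest and AEs leading to discontinuation.

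**Working it through.** The plan gives no figure to reproduce. The check is to trace the rules and then bound their reach.

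**1. The phase rule, branch by branch (LTE entrants, SAP 7.1.5.2 with SAP 3).**

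| Onset date | Stop date | Phase | Counted in an AE table if treatment-emergent? |
|---|---|---|---|
| Partial, before month/year (or year) of first LTE dose | any | Main Study | Yes |
| Partial, after it | any | LTE | No; onset known to be in the LTE |
| Missing, or partial and equal to it | before first LTE dose | Main Study | Yes |
| Missing, or partial and equal to it | missing, same or later | LTE | **No; phase not known** |

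**2. Every AE in the last row is treatment-emergent.** If onset is missing, the stop date is either missing or not before the first LTE dose, hence after the first study dose; both cases qualify. If onset is partial and equal to the month/year (or year) of first LTE dose, it is not before that of the first study dose and not after that of last dose plus 30 days.

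**3. Such an AE may have begun in the Main Study.** Assumed example: first LTE dose on 28 March, onset recorded only as March, event ongoing. Days 1 to 27 of the month precede the LTE dose, so 27 of 31 possible onset days (87%) are Main Study days. The AE still goes to the LTE.

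A second assumed case, with no stop date: first dose 10 March 2020, first LTE dose 112 days later on 30 June 2020.

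- Onset missing, 2020 only, or June 2020: LTE.
- Onset March 2020 or May 2020: Main Study.
- Stop date changed to 15 June 2020: the missing, 2020-only and June 2020 onsets all return to the Main Study.

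**4. How often a true Main Study onset would be sent to the LTE.** Assumptions: onsets spread evenly over 112 Main Study days, no stop date, and each of 365 start dates in turn. The share sent to the LTE is the number of Main Study days in the same calendar month (or year) as the first LTE dose, divided by 112.

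- Month-only onset: about 13% on average, range 0% to 27%. The maximum is 30/112 = 26.8%. The 30 June case gives 29/112 = 25.9%.
- Year-only onset: about 85% on average, range 0% to 100%.
- Completely missing onset: 100%.

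**5. Ceiling on subjects.** 13/67 = 19.4%. This counts LTE entrants, not subjects with a qualifying date.

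**6. Effect on one table row.** Arm sizes at termination are not given. If 67 subjects split 2:2:1:2, the arms hold 67 × 2/7 = 19.1, 19.1, 67 × 1/7 = 9.6 and 19.1. One subject is then 1/19 = 5.3 points, or 1/10 = 10 points under adalimumab. SAP 7.1.6.1 counts a subject once per summary, so the shift occurs only if that subject has no other event in the row.

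**The case against.** **Nothing is lost from reporting.** This stands. The events are in the all-AE listing with their flag and, where they qualify, in the listings of serious AEs, Grade 3 or higher AEs, AEs leading to discontinuation and AEs of special interest. The gap is in the counts.

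**The rule is not one-sided.** A reader might infer that any missing or partial onset goes to the LTE, or that the doubtful event is always removed. Neither is so: the first and third rows of the table keep such events in the Main Study, and most month-only dates are safe.

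**Treatment emergence and phase are separate rules.** A reader might say that the SAP contradicts itself. It does not; both rules can be applied as written. The difficulty arises only when they are combined with tables restricted to the Main Study.

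**Few such dates should exist.** AEs are collected at every visit (Protocol Appendix 2), queries are resolved or closed before the final analysis (SAP 2.1), and serious AEs are reconciled with the safety database (SAP 7.1.4). This is fair.

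**The opposite default can misattribute.** This is the strongest point. Placebo and adalimumab subjects all switch to filgotinib in the LTE. Moving their doubtful events to the Main Study may charge a filgotinib event to a control arm and dilute a safety signal. With a completely missing onset, the event could have begun at any time in the LTE. The objection has force, but within limits. Filgotinib entrants stay on the same drug, 7 of the 13 entrants left at once, and the present rule does not count the event under filgotinib either, because it counts it nowhere. The objection calls for a separate count of switched subjects, which the fix includes.

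**Conclusion.** The point holds in a narrow form and is minor. For LTE entrants, a treatment-emergent AE that may have begun on randomised treatment can be absent from every AE summary table when its onset is completely missing, or matches the month/year (or year) of the first LTE dose, and no earlier stop date exists.

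The reach is at most 13 of 67 subjects. A reader might take 19.4% as the share affected, but it is only a ceiling: the documents give no count of incomplete dates, and the number may be zero. The shift of about 5 or 10 points per subject rests on an assumed arm split and on the subject having no other event in the row.

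Two wider inferences are also unsupported. The LTE is not without tables, since SAP 4.1 tabulates disposition by phase with reasons for stopping. Nor are the AE tables the only safety comparison by arm, since SAP 7.2 and 7.3 provide laboratory, liver, blood count and vital sign summaries.

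**What to change.** Add to SAP 7.1.5.2: for the Main Study AE tables, a treatment-emergent AE in an LTE entrant with a missing or incomplete onset date is allocated to the Main Study unless its known onset month and year (or year) is after that of the first LTE dose. Fully dated events stay under SAP 7.1.5.1.

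Flag the reallocated events in the listing. Footnote their number by arm in the AE tables, with placebo and adalimumab subjects who switched to filgotinib shown separately, so that the tables can be read with and without them.

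The cost is one sentence, one line of derivation code and a footnote. SAP 1 already provides for changes after finalization to be documented in the CSR. The allocation would no longer match the parallel rule for concomitant medications in SAP 7.4.2, which can stay as it is because the change concerns AE tables only. The downside is that an event that began on filgotinib in the LTE may be counted under placebo or adalimumab; the short LTE exposure limits this and the footnote makes it visible.
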